7.4 Blinding

This study is single-blind.

7.5 Study Plan

7.5.1. Screening

At this clinic visit the subject will undergo the following evaluations:

- Sing Informed Consent.
- Demographics will be collected.
- A medical, pain and surgical history will be collected.
- Subjects will be asked to fill out VAS questionnaire.
- Medication use will be collected.
- Eligibility criteria will be evaluated.

All applicable information will be documented on a CRF.

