7.2 Randomization Process

The clinical investigation will be single-blind. The assignment to the type of surgical treatment is carried out randomly and open for the investigators but not for

the patients. Randomization will be done with concealment of the randomization sequence and it takes place after informed consent has been signed.

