7.5.2. Baseline* (within 30 days from Screening Visit)

At this clinic visit the subject will undergo the following evaluations:

- Randomization.
- Eligibility criteria will be re-evaluated.
- Any change of medication will be collected.

- Subjects will be asked to fill out standard questionnaires to assess (VAS, ODI, SF-12 and DN4).
- Subjects will be assessed for possible adverse events, if any.
- AP and lateral view lumbar imaging.
- Screening failures will be collected.

*Baseline and Treatment visits could be at the same time.

All applicable information will be documented on a CRF.

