7.6 Evaluation Endpoints

▪ Primary endpoint

Visual Analogue Scale (VAS): The VAS measures the pain intensity reported by the subject. Subject scores the intensity of pain on a 10 mm line. The VAS in this study consists of a 10 mm line with one indicating “No Pain” and the other end indicating “Worst imaginable pain”. Upon completion by the subject VAS scores will be measured and converted to a numeric value (0.0 mm to 10.0 mm) by site staff personnel. VAS is the most widely used outcome measure in assessing pain due to its documented reliability and validity, ease in administration, and minimal training requirements for the administrator.

Subjects will complete a mean VAS score for leg and back pain: at Baseline, months 1, 2, 4, 6 and if applicable at the Unscheduled visit. The change in leg and back pain VAS scores, the percentage change in leg and back pain VAS scores, and the responder rate for leg and back pain will be calculated and summarized for each visit.

▪ Secondary Endpoints.

- Oswestry Disability Index (ODI): The ODI measures functional disability as reported by the subject. Subjects will complete ODI during the study visits: at Baseline, months 1, 2, 6 and if applicable at the Unscheduled visit. The changes in functional disability will be summarized as continuous variables.

- Short Form Health Survey (SF-12): The SF-12 measure health status reported by subject at: Baseline, months 1, 2, 4, 6 and if applicable at the Unscheduled visit. The changes in health status will be summarized as continuous variables.

- Douleur Neuropathique 4 Questions (DN4): The DN4 measures the neuropathic pain reported by the subject. Subjects will complete DN4 during the study visits: at Baseline, months 1, 2, 6 and if applicable at the Unscheduled visit. The changes in neuropathic pain will be summarized as continuous variables.

- Patient Impression of Improvement questionnaire (PGI-I): The PGI-I measure subjective improvement in pain. Subjects will complete PGI-I form during the study visits at: month 1, 2, 4, 6 and if applicable at the Unscheduled visit.

- Medication Usage: morphine equivalent units of opioid medications; other non-opioid pain medications. Assessed at: Baseline, months 1, 2, 4, 6 and if applicable at the Unscheduled visit.

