7.10 Definition of Population for Analyses

We define 3 different subject populations for analysis:

1. Intent-to-Treat (ITT)

- All subjects who receive any treatment of the groups (Experimental or Control)

2. Per Protocol (PP)

- All subjects who receive treatment of the study and complete the Primary Effectiveness Assessment (Primary Endpoint defined above).

3. ITT-Baseline (ITT-B)

- All subjects who complete baseline assessment. In order to capture AEs that occur prior to the 6 months follow-up visit.

8. – SAFETY ASPECTS

The definitions presented in this section allow for a clear understanding of adverse event data collection and reporting requirements.

Medical Device

Any instrument, apparatus, implement, machine, appliance, implant, software, material or other similar or related article.

Intended by the manufacturer to be used, alone or in combination, for human beings for one or more of the specific purpose (s) of:

- Diagnosis, prevention, monitoring, treatments or alleviation of disease,
- Diagnosis, monitoring, treatment, alleviation of, or compensation for, an injury,
- Investigation, replacement, modification, or support of the anatomy or of a physiological process,
- Supporting or sustaining life,
- Control of conception,
- Disinfection of medical devices and

Which does not achieve its primary intended action in or on the human body by pharmacological, immunological or metabolic means, but which may be assisted in its intended function by such means. The term 'medical device' is usually defined by national regulations.

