The Sponsor contact information for these events is:

[name] [name],

E-mail: [contact]

Table1. Schedule

Assessment								
Visit	Screening	Baseline	Treatment	1 month	2 months	4 months	6 months	Unscheduled
Window		Within 30 days from screening	± 15 days	± 7 days	± 14 days	± 14 days	± 20 days	
Pregnancy Test	X							
Sign Informed Consent	X							
Entry Criteria Evaluation	X	X						
Demographics	X							
Medical History	X	X						
Randomization		X						
Treatment Process			X					
Pain and Surgical History	X							
Medication Usage	X		X	X	X	X	X	X
VAS questionnaire		X		X	X	X	X	X
ODI questionnaire		X		X	X		X	X
SF-12 questionnaire		X		X	X	X	X	X
DN4 questionnaire		X		X	X		X	X
PGI-I questionnaire				X	X	X	X	X
Subject questionnaire of treatment satisfaction					X		X	X
AP and Lateral radiography imaging		X						
Deviation Monitoring			X	X	X	X	X	X
Adverse Event Monitoring		X	X	X	X	X	X	X
Screening Failures		X						
Study Completion			X				X	X

9. - TREATMENT DESCRIPTION

Both treatments (control group and experimental group) will always be performed in an ambulatory environment through sedation and anaesthesia.

The lower back and buttocks will be prepared for an aseptic technique. Lateral and AP views of the sacral foramina and hiatus will be taken and the entry point for the epidural needle will be marked on the surface of the skin, 1-2 cm caudal to the sacral hiatus. The skin and subcutaneous tissue underlying the entry site will be anesthetized using 1-2 ml of 1% lidocaine.

A 9-cm-long, 16-gauge (ga) epidural needle (Cosman RCE-C916S-P) is inserted through the skin and into the caudal canal, 1-2 cm beyond the sacral hiatus, ending at an angle of approximately 15° concerning the skin. Intravascular and subdural placement will be ruled out by injecting 1-1.5 ml of non-ionic radiographic contrast (180 mg of iohexol per ml) through the fluoroscopic needle *in vivo*.

9.1 Control Group. Epidural Steroids Injection.

A radiopaque, guidable radiofrequency electrode (Cosman RCE-E401519-P) will bend slightly at a 45° angle proximal to its metal tip and then be inserted through the needle. The electrode shall include an active 20/15 mm gauge tip, a 19/40 cm gauge shaft, a rounded distal point temperature sensor, an injection port and an integral generator connection. The electrode will be visualized by fluoroscopy as it is guided in the epidural space from the sacral canal to the lumbar vertebral canal.

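### The plan does not require eligibility and baseline measures to be completed before allocation is known, and its treated-only ITT set drops anyone excluded in between

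*Combined protocol and SAP*

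**What the plan says.** **Order at the Baseline visit.** Section 7.5.2 names randomisation first. Next comes "Eligibility criteria will be re-evaluated", and after that the baseline VAS, ODI, SF-12 and DN4. Screening failures are recorded at the same visit.

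**Precondition and knowledge of the arm.** Section 7.2 says of randomisation that "it takes place after informed consent has been signed". It does not mention confirmed eligibility. The sequence is concealed, and the assignment is known to investigators but not to patients.

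**Analysis set.** Section 7.10 defines the ITT set as "All subjects who receive any treatment of the groups (Experimental or Control"). Per Protocol also requires treatment. ITT-B requires only a completed baseline, but its stated purpose is to capture adverse events. Section 13 does not name the set for the primary comparison.

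**VAS schedule.** Section 7.5.1 (Screening) lists both "Subjects will be asked to fill out VAS questionnaire" and "Eligibility criteria will be evaluated". In Table 1 the row "VAS questionnaire" is blank at Screening and starts at Baseline, while the row "Entry Criteria Evaluation" is marked at both visits. Section 7.6 agrees with Table 1: "Subjects will complete a mean VAS score for leg and back pain: at Baseline, months 1, 2, 4, 6". The VAS entry criterion in section 6.1 does not name the visit at which it must be met.

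**The concern.** Concealment protects the assignment until it is made. It does not protect a decision taken afterwards by someone who knows the arm. If the eligibility re-check follows randomisation, a borderline patient can be kept in one arm and excluded from the other.

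The VAS threshold is one route. Section 6.2 also has an exclusion that rests on the investigator's opinion of medical, social or psychosocial factors, which leaves more room for judgement.

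Such exclusions happen before treatment, so neither the ITT set nor the Per Protocol set would contain them. The comparability that randomisation provides would be lost in a way that the efficacy analysis could neither show nor repair.

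**Working it through.** **1. The plan's own figure.** Inputs from section 7.3: difference 60 − 40 = 20 mm, SD 30 mm, two-sided 5%, power 90%, losses 20%. The exact t-test needs 48.26, so 49 per group; 49 / 0.80 = 61.25, so 62. The stated 62 per group is reproduced and this point does not alter it.

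**2. Can a decision follow a known allocation?**

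| Question | Where | Answer |
|---|---|---|
| Must eligibility be confirmed before randomisation? | 7.2, 7.5.2 | Not stated; only consent is |
| Is eligibility judged at the randomisation visit? | 7.5.2, Table 1 | Yes |
| Do those judging it know the arm once it is assigned? | 7.2 | Yes |
| Is a subject excluded before treatment in the ITT set? | 7.10 | No |

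The plan permits the sequence but does not prescribe it.

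**3. Does the missing Table 1 mark matter here?** Suppose the VAS is marked at Screening. Section 7.5.2 still re-checks eligibility and logs screening failures at the randomisation visit, so all four answers are unchanged.

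**4. Size, illustration A: exclusion on baseline VAS in one arm.** Assumed: a fraction f of 5% or 10% is dropped from the bottom of a normal baseline distribution with SD 15 mm.
- Shift in the arm's baseline mean = φ(z_f)/(1 − f) SD. At 5%: 0.1031/0.95 = 0.109 SD. At 10%: 0.1755/0.90 = 0.195 SD.
- In mm: 0.109 × 15 = 1.6 and 0.195 × 15 = 2.9.
- Change score, with correlation 0.5 and equal SDs at both visits (slope 0.5): × (1 − 0.5) = 0.8 and 1.5 mm, in favour of the arm with exclusions.
- Standard error with 49 per arm and the plan's 30 mm SD kept for the change: 30 × √(2/49) = 6.06 mm. Two-sided rejection under no effect: about 5.2% and 5.7%.

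The last step mixes two assumptions. Equal SDs of 15 mm with correlation 0.5 imply a change SD of √(225 + 225 − 225) = 15 mm, and the same biases then give 5.8% and 7.7%. A change SD of 30 mm with slope 0.5 fits a follow-up SD of 30 mm and correlation 0.25: √(225 + 900 − 225) = 30.

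Why not a baseline SD of 30 mm? Reading 5 points as 50 mm on a 100 mm scale, eligible values lie between 50 and 100 mm, so their SD cannot exceed 25 mm. For 5% or 10% of a normal distribution with SD 30 mm to fall below 50 mm, its mean would have to be 50 + 1.645 × 30 = 99 mm or 50 + 1.282 × 30 = 88 mm, which is not credible.

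**5. Size, illustration B: exclusion on anything else.** If a fraction f of one arm is excluded and its mean outcome differs by d from those kept, that arm's mean shifts by d × f/(1 − f). For assumed d of 10 to 30 mm: 0.5 to 1.6 mm at 5%, and 1.1 to 3.3 mm at 10%.

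**6. Effect of adjustment.** In illustration A, selection acts only through baseline VAS. Under a linear relation, regression on baseline VAS removes the bias; a simulation of that scenario gave a bias of about 0. In illustration B it removes only the part that baseline VAS explains.

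**The case against.** **Bullet lists are not sequences.** This is fair. Nothing says the section 7.5.2 list is chronological, and Table 1 puts the pregnancy test above consent although consent must come before any procedure. A competent site may well confirm eligibility first. What stands is that no sentence requires it.

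**The trial is not open to everyone.** Patients are blinded, the sequence is concealed, and the patient marks the VAS while staff only measure it (section 7.6). Staff knowledge therefore bears on who is kept more than on the VAS value itself. The DN4 is less protected, because its last two questions rest on the doctor's examination.

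**Exclusions would not vanish entirely.** Screening failures are logged, and ITT-B would keep an untreated patient who completed baseline. But ITT-B has no stated efficacy role. The plan also does not say what happens to a patient who fails the re-check after randomisation; that such a patient goes untreated is an inference.

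**Section 13 already provides regression for imbalance.** It does, but only if imbalance is observed, and it cannot bring back excluded patients.

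**A stronger reading.** A reader might infer from Table 1 that no VAS exists before the randomisation visit, so that the entry check is forced to that visit. The documents do not support this. Section 7.5.1 schedules both a VAS and an eligibility evaluation at Screening, Table 1 itself marks entry criteria there, and no rule says that the table overrides the text.

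**Conclusion.** The concern holds as a gap in the required order of steps, combined with an ITT definition that omits untreated randomised subjects. The plan allows allocation-aware exclusion; it neither instructs it nor shows that it occurred.

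The VAS schedule conflict between section 7.5.1 on one side and Table 1 and section 7.6 on the other is a secondary contradiction.

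The numerical effect is probably small. Illustration A gives a bias of about 0.8 to 1.5 mm against a planned difference of 20 mm, with type I error of about 5.2% to 5.7% at a change SD of 30 mm (up to 7.7% if that SD were 15 mm), and less after baseline adjustment. The exclusion fraction, baseline SD and correlation are all assumed. The main reason to act is that the plan's efficacy sets could not reveal or correct such exclusions.

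**What to change.** - **Sections 7.2 and 7.5.2:** make randomisation the last Baseline step. Release the allocation only after eligibility is confirmed and recorded and the baseline VAS, ODI, SF-12 and DN4 are complete.
- **Section 7.10:** define the ITT set as every randomised subject, analysed in the assigned arm, and name it for the primary comparison. Seek the 6-month VAS from any subject randomised but not treated.
- **Sections 7.5.1, 7.6 and Table 1:** reconcile the VAS schedule and state at which visit the VAS entry criterion is checked. Correcting the table alone would not close the gap.

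The cost is a few sentences and one table entry. The sample size does not change, no visit is added, and Baseline and Treatment can still fall on the same day. With the order fixed, few subjects should be randomised without being treated, so the wider ITT set adds little follow-up work.

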7.5.2. Baseline* (within 30 days from Screening Visit)

At this clinic visit the subject will undergo the following evaluations:

- Randomization.
- Eligibility criteria will be re-evaluated.
- Any change of medication will be collected.

- Subjects will be asked to fill out standard questionnaires to assess (VAS, ODI, SF-12 and DN4).
- Subjects will be assessed for possible adverse events, if any.
- AP and lateral view lumbar imaging.
- Screening failures will be collected.

*Baseline and Treatment visits could be at the same time.

All applicable information will be documented on a CRF.

7.5.3. Treatment Visit (\pm 15 days)

At this clinic visit the subject will undergo the following evaluations:

- Treatment process.
- Study completion (if applicable).
- Adverse event monitoring.
- Deviation monitoring.
- Any change of medication will be collected.

7.5.4. 1 Month Visit (\pm 7 days)

At this clinic visit the subject will undergo the following evaluations:

- Any change of medication will be collected.
- Subjects will be asked to fill out standard questionnaires to assess (VAS, ODI, SF-12, DN4 and PGI-I).
- Subjects will be assessed for possible adverse events, if any.
- Adverse event monitoring.
- Deviation monitoring.

All applicable information will be documented on a CRF.

7.5.5. 2 Months Visit (\pm 14 days)

At this clinic visit the subject will undergo the following evaluations:

- Any change of medication will be collected.
- Subjects will be asked to fill out standard questionnaires to assess (VAS, ODI, SF-12, DN4 and PGI-I).
- Subjects will be assessed for possible adverse events, if any.
- Adverse event monitoring.
- Deviation monitoring.
- Subject questionnaire of treatment satisfaction.

All applicable information will be documented on a CRF.

7.5.6. 4 Months Visit (\pm 14 days)

At this clinic visit the subject will undergo the following evaluations:

- Any change of medication will be collected.
- Subjects will be asked to fill out standard questionnaires to assess (VAS, SF-12 and PGI-I).
- Subjects will be assessed for possible adverse events, if any.
- Adverse event monitoring.
- Deviation monitoring.

All applicable information will be documented on a CRF.

7.5.7. 6 Months Visit (\pm 20 days)

At this clinic visit the subject will undergo the following evaluations:

- Any change of medication will be collected.
- Subjects will be asked to fill out standard questionnaires to assess (VAS, ODI, SF-12, DN4 and PGI-I).
- Subjects will be assessed for possible adverse events, if any.
- Adverse event monitoring.
- Deviation monitoring.
- Subject questionnaire of treatment satisfaction.

All applicable information will be documented on a CRF.

7.5.8. Unscheduled Visit

At this clinic visit the subject will undergo the following evaluations:

- Any change of medication will be collected.
- Subjects will be asked to fill out standard questionnaires to assess (VAS, ODI, SF-12, DN4 and PGI-I).
- Subjects will be assessed for possible adverse events, if any.
- Study completion (if applicable).
- Adverse event monitoring.
- Deviation monitoring.
- Subject questionnaire of treatment satisfaction.

All applicable information will be documented on a CRF.

7.6 Evaluation Endpoints

▪ Primary endpoint

Visual Analogue Scale (VAS): The VAS measures the pain intensity reported by the subject. Subject scores the intensity of pain on a 10 mm line. The VAS in this study consists of a 10 mm line with one indicating “No Pain” and the other end indicating “Worst imaginable pain”. Upon completion by the subject VAS scores will be measured and converted to a numeric value (0.0 mm to 10.0 mm) by site staff personnel. VAS is the most widely used outcome measure in assessing pain due to its documented reliability and validity, ease in administration, and minimal training requirements for the administrator.

Subjects will complete a mean VAS score for leg and back pain: at Baseline, months 1, 2, 4, 6 and if applicable at the Unscheduled visit. The change in leg and back pain VAS scores, the percentage change in leg and back pain VAS scores, and the responder rate for leg and back pain will be calculated and summarized for each visit.

▪ Secondary Endpoints.

- Oswestry Disability Index (ODI): The ODI measures functional disability as reported by the subject. Subjects will complete ODI during the study visits: at Baseline, months 1, 2, 6 and if applicable at the Unscheduled visit. The changes in functional disability will be summarized as continuous variables.

- Short Form Health Survey (SF-12): The SF-12 measure health status reported by subject at: Baseline, months 1, 2, 4, 6 and if applicable at the Unscheduled visit. The changes in health status will be summarized as continuous variables.

- Douleur Neuropathique 4 Questions (DN4): The DN4 measures the neuropathic pain reported by the subject. Subjects will complete DN4 during the study visits: at Baseline, months 1, 2, 6 and if applicable at the Unscheduled visit. The changes in neuropathic pain will be summarized as continuous variables.

- Patient Impression of Improvement questionnaire (PGI-I): The PGI-I measure subjective improvement in pain. Subjects will complete PGI-I form during the study visits at: month 1, 2, 4, 6 and if applicable at the Unscheduled visit.

- Medication Usage: morphine equivalent units of opioid medications; other non-opioid pain medications. Assessed at: Baseline, months 1, 2, 4, 6 and if applicable at the Unscheduled visit.

- 5-point scale where 1 is “very satisfied” to 5 that is “very dissatisfied”; their charging convenience and remote control use during the study visits: Months 2, 6 and if applicable at the Unscheduled visit. The responses will be summarized. Study personnel will be appropriately trained for administration of each test.

- Safety (device and procedures): Safety will be assessed by characterizing clinically meaningful change in adverse events at all study visits and in related to medical device or procedures.

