5.2 Primary Endpoint

Difference in pain reduction between the control group and the experimental group since the baseline visit and the 6 month visit evaluated by Visual Analogue Scale (VAS).

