6.1 Inclusion Criteria

1. Men and women over 18 years old.
2. Written informed consent according to ICH/GCP and Spanish legislation, obtained before any study procedure.
3. Pain VAS score at least 5 points.
4. Duration of pain at least 3 months after back surgery with conservative treatment.
5. Leg-dominant radicular pain deemed neuropathic based on clinical history and examination.
6. Responsive to selective radicular nerve block (bupivacaine 0.125%).
7. Patients who have had a previous epidural steroid injection.

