7.3 Sample Size and justification

Pain reduction at least thirty millimeters between the baseline visit and the 6 months visit in patients assigned to the experimental group evaluated by the Visual Analogue Scale (VAS). Pain reduction of twenty millimeters less in the experimental group than in the control group since the baseline visit and the 6 months visit evaluated by the Visual Analogue Scale (VAS).

To achieve a power of 90.00% to detect differences in the contrast of the null hypothesis $H_0: \mu_1 = \mu_2$ through a bilateral T-Student Test for two independent samples, taking into account that the level of significance is 5%, and assuming that the mean of the difference in VAS of the 6-month radiofrequency plus steroid group is 40 mm, the average of the control group is 60 mm and the standard deviation of both groups is 30 mm, with an estimate of losses of the 20%, it will be necessary to include 62 patients per group, total of 124 patients.

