11.1 Insurance Policy

According with current clinical trial legislation, this clinical trial does not require an insurance policy since the devices under study are used under the authorized conditions of use and the study does not imply an increase in the risk to the patient.

12. - PUBLICATIONS RIGHTS

Principal Investigator shall have the right to publish the results of the Study in any abstract, paper, presentation or manuscripts (not limited enumeration).

Principal Investigator shall give BOSTON SCIENTIFIC a reasonable period of 30 (thirty days) to review and comment upon an intended publication of Principal Investigator regarding the results of the Study prior to publication, to determine if any Intellectual Property Rights and/or Confidential Information should be removed. BOSTON SCIENTIFIC shall respond promptly in writing to Principal Investigator with any comments or objections, setting forth such information in reasonably sufficient detail.

Principal Investigator shall consider BOSTON'S SCIENTIFIC comments and/or objections in good faith and shall cause any and all appropriate changes to be made prior to further distribution and publication.

13. - STATISTIC ANALYSIS

A descriptive analysis of the categorical variables was performed using absolute and determined frequencies; and in the numerical variables, through the mean and

standard or median deviation and 25th and 75th percentiles, according to compliance with the assumption of normality.

The analysis of the main variable, pain difference between baseline measurement and 6 months after treatment in the radiofrequency group plus steroids vs steroids, will be carried out using a contrast of means with the t-Student or U Mann-Whitney test in case of not being able to fulfill the corresponding assumptions.

The size of the effect is estimated with Cohen's letter, interpreting a Cohen's letter <0.01 as "very small", between 0.01 to 0.2 as a "small" effect, around 0.5 an "average" effect ", from 0.8 to infinity, a" large "effect, according to the categorization of Cohen and Sawilowsky (Cohen, Jacob (1988). Statistical analysis of power for behavioral sciences. Routledge; Sawilowsky, S (2009). "New effect size rules of thumb". Journal of Modern Applied Statistical Methods. 8 (2): 467–474.).

If the imbalance is observed between the two groups, linear regression will be executed to adjust for variables that are observed unbalanced between them.

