15.2.1. Visual Analogue Scale (VAS)

VIAUSAL ANALOGUE SCALE (VAS) OF PAIN

Sponsor: Fundación Investigación HM Hospitales

Principal Investigator: [name] [name]

Protocol Code: EPIPUL

Form Version: 1.0 of 26th of July 2019

Pain assessment

Instructions: Place a vertical bar (|) in the place of the line that describes the average pain that have you felt in the last 7 days.

PAIN BACK

No Pain _____ The worst pain imaginable _____

Patient marked average (cm):

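### The primary VAS has no defined pain site: the protocol enrols leg-dominant radicular pain, lists leg and back without ranking them, and its VAS form as reproduced shows only a back-pain line

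*Combined protocol and SAP*

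**What the plan says.** - **Primary endpoint (5.2, and the same in the Summary):** "Difference in pain reduction between the control group and the experimental group since the baseline visit and the 6 month visit", measured by VAS. No body site is given.
- **Sample size (7.3):** "assuming that the mean of the difference in VAS of the 6-month radiofrequency plus steroid group is 40 mm", with 60 mm in the control group and an SD of 30 mm. No site is given.
- **Analysis (Section 13):** the main variable is the "pain difference between baseline measurement and 6 months after treatment in the radiofrequency group plus steroids vs steroids". No site is given.
- **Operational definition (7.6):** "Subjects will complete a mean VAS score for leg and back pain". The section then lists change and percentage change for leg and back, and adds that "the responder rate for leg and back pain will be calculated and summarized for each visit". Neither site is ranked.
- **VAS form (Annex II, 15.2.1):** the patient marks the place on the line that "describes the average pain that have you felt in the last 7 days". As it reads in the available text, the form has one line, headed for back pain, and one result field.
- **Population (6.1):** "Leg-dominant radicular pain deemed neuropathic based on clinical history and examination", and "Pain VAS score at least 5 points", the latter again without a site. The hypothesis in 5.1 concerns chronic lumbar radicular pain.

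**The concern.** The hypothesis and the entry criteria point to leg pain, section 7.6 treats leg and back alike, and the form as it reads measures back pain. No passage reconciles the three. The word *mean* in 7.6 adds a further ambiguity: it may be the 7-day average that the form asks for, or a leg/back composite.

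Two things are at stake. If the form is used as it reads, leg-pain intensity is lost for good and the radicular-pain hypothesis cannot be tested directly. The other instruments do not replace it: the pain-intensity item of the ODI names no site and its instructions concern back problems, and the DN4 records yes/no qualities, not intensity. If both sites are collected, nothing in the plan prevents the primary variable from being picked after the results are known.

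**Working it through.** **1. The plan's own figure.** Inputs from 7.3: difference 60 − 40 = 20 mm, SD 30 mm, two-sided 5%, power 90%, losses 20%. The two-sample t-test (noncentral t) with standardised effect 20/30 = 0.667 needs 48.26, so 49 evaluable per group. Then 49 / (1 − 0.20) = 61.25, so 62 per group and 124 in total. The stated size is reproduced, and power with 49 per group is 90.4%. The arithmetic is not in question; what it refers to is.

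**2. Power if the analysed score is not leg pain.** Assumptions: the 20 mm and 30 mm figures belong to leg pain; SD 30 mm at each site; 49 evaluable per group; back effect *b* and correlation *r* between sites unknown, so varied.

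- Back only: effect *b*, SD 30, noncentrality (*b*/30) × √(49/2).
- Leg/back average: effect (20 + *b*)/2, SD 30 × √((1 + *r*)/2), which is 24.2, 26.0 or 27.7 mm for *r* = 0.3, 0.5 or 0.7.

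| Back effect *b* (mm) | 0 | 5 | 10 | 15 | 20 |
|---|---|---|---|---|---|
| Back only | 5.0% | 12.9% | 37.2% | 68.8% | 90.4% |
| Average, *r* = 0.3 | 52.6% | 71.6% | 86.0% | 94.4% | 98.2% |
| Average, *r* = 0.5 | 47.1% | 65.5% | 80.8% | 91.0% | 96.5% |
| Average, *r* = 0.7 | 42.5% | 60.0% | 75.7% | 87.3% | 94.3% |

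The average matches leg-only power when (20 + *b*)/2 divided by 30√((1 + *r*)/2) equals 20/30, that is *b* = 40√((1 + *r*)/2) − 20. This gives 12.2, 14.6 and 16.9 mm for *r* = 0.3, 0.5 and 0.7. Below these values averaging loses power; above them it gains.

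**3. False positives if the site is chosen afterwards.** No true effect at either site, each tested two-sided at 5%, 49 per group, 200,000 simulated trials per correlation:

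| Correlation *r* | 0.3 | 0.5 | 0.7 |
|---|---|---|---|
| Leg or back significant | 9.4% | 9.0% | 8.4% |
| Leg, back or their average significant | 10.5% | 9.6% | 8.7% |

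For two independent sites the rate would be 1 − 0.95² = 9.75%. Repeat simulations agree to within about 0.2 percentage points.

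**The case against.** - **The leg line may have been lost when the PDF was read.** The form is a drawn line, and 7.6 plans leg summaries that need leg data. This stands: the form is a query to settle against the original, not a proven error. The gap in 5.2, 7.3, 7.6 and 13 remains even if the form has both lines, because two scores with no ranking leave the choice open.
- ***Mean* is more naturally the 7-day average.** Patients complete the score themselves, the form asks for an average over time, and 7.6 goes on to speak of scores in the plural. This is the likelier reading. It gives two separate scores and still no primary.
- **The power figures prove no loss.** Correct. They rest on assumed back effects and correlations, include gains, and assign the 20 mm and 30 mm to leg pain, which the documents do not do. Section 4 describes the syndrome as back or leg pain, so a back effect close to the leg effect is possible. The case rests on the undefined variable and the selection risk.
- **The false-positive rate counts both directions.** Restricted to a false claim in favour of radiofrequency, it is roughly 4.2–4.8% against 2.5%. The near-doubling is the same, and the plan's own test is two-sided at 5%.
- **The choice of site belongs to the sponsor.** The sponsor may define another single variable. Leg pain is the choice that follows from the protocol's own hypothesis and entry criterion.

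**Conclusion.** The concern holds and must be fixed before the analysis, and before further data collection if the original form has no leg line. No passage defines the site of the primary VAS, and the passages that bear on it point in different directions. This is more than missing detail: followed as written, the plan either records a site that the hypothesis does not target or leaves the confirmatory test open to choice after the data are seen.

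The firmest measure of size is the false-positive rate of about 8.4–9.4% instead of 5%, given free choice between two sites correlated at 0.7 to 0.3. The power consequence is undetermined. It could be severe (5% for a back-only score with no back effect) or nil (90.4% with a back effect of 20 mm). Confidence is high on the missing definition. Whether leg pain goes unrecorded depends on the original form.

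**What to change.** 1. In 5.2, 7.6 and 13, name leg-pain VAS (average of the last 7 days), change from baseline to 6 months, as the single primary variable, with back-pain VAS secondary.
2. In 7.6, state that *mean* is the 7-day average and that leg and back are two separate scores.
3. Check the original Annex II form; if it has no leg line, issue a new version with one.
4. State which site the 20 mm difference and 30 mm SD (7.3) and the VAS entry threshold (6.1) refer to.
5. Reconcile the screening VAS: 7.5.1 asks for one, but Table 1 shows none, and eligibility is evaluated at that visit.

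The cost is protocol wording and, if the form must change, one extra mark at each of the five scheduled VAS visits in 7.6 (baseline and months 1, 2, 4 and 6), or six if the screening VAS is kept. The 62 per group stands if the 20 mm and 30 mm figures refer to leg pain; otherwise 7.3 must be redone with leg-pain figures.
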